## **6.0 Reporting of Adverse Events or Unanticipated Problems involving Risk to Participants or Others**

Serious adverse events resulting in any physical harm associated with testing will be reported to the IRB within 24 hours; minor adverse events (e.g. nausea, infusate infiltration, discomfort associated with infusion) will be reported to the Alcohol Studies DSMB meeting at least annually.

## **6.0 Study Withdrawal/Discontinuation**

The participant may withdraw from the study at any time for any reason, and will be paid an amount pro-rated to the duration of their participation on the testing day, including time to recover to a BrAC < 35 mg/dL. The PI may choose to terminate any subject's participation at any time if it is deemed that s/he cannot participate or cooperate in testing procedures safely, with the same pro-rated compensation to the subject.

## **7.0 Statistical Considerations**

### **Aim 1: Characterize SDA across lifetime drinking history.**

#### Aim 1 Hypothesis Testing Plan

[figure not shown]
*Hypothesis 1: Greater SDA will reflect greater lifetime drinking.* We will conduct a linear mixed-model analysis, with lifetime drinking history as the continuous independent variable and with SDA as the dependent variable. Lifetime drinking history will be defined as the kg of alcohol reported consumed via the Concordia Lifetime Drinking Questionnaire. SDA will be defined as the amount of work performed (cumulative number of SDA trials completed) for alcohol rewards in the aversive session. Age, gender, recent drinking history, and race will be included as covariates, due to their relationship with AUDs.

**Hypothesis 2:** Those with a high lifetime drinking history will demonstrate less sensitivity to aversion in the preference to work for alcohol. Specifically, those with a high lifetime drinking history will work more for alcohol compared to water under both neutral and aversive conditions, whereas those with a low lifetime drinking history will only work more for alcohol compared to water in the neutral session. We will conduct a mixed linear model in which lifetime drinking history is the independent variable, as in hypothesis 1, but using a different dependent measure. We will subtract work for water from work for alcohol, dividing the difference by the sum of the work done for alcohol plus water (separately under the aversive stimulus ( $R_a$ ) and under the neutral stimulus ( $R_n$ )). The ratios  $R_a$  and  $R_n$  will be used as the repeated measures dependent variables, and lifetime drinking history (high vs. low), stimulus type (aversive vs. neutral) and their interaction will be independent variables. Covariates will include age, gender, recent drinking history, and race. If lifetime drinking history and the interaction with stimulus are significant predictors of the ratios of work performed, we will conduct follow-up planned contrasts to examine the ratios separately for the neutral and aversive sessions to test high and low lifetime drinking history.

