#### Aim 2 Hypothesis Testing Plan.

**Hypothesis 3:** Those with greater SDA will have greater AUD severity, greater LDH, greater negative urgency, greater density of familial history of alcoholism, and reduced subjective, behavioral, and electrophysiologic sensitivity to alcohol. To minimize error inflation from multiple univariate tests, we will use structural equation modeling (R3.01 data analysis software using the lavaan statistical package; Figure 6). We will examine AUD severity as an observed independent variable of AUD symptom count. Lifetime Drinking History and density of family history of alcoholism will be observed variables, computed with information collected with Concordia Lifetime Drinking Questionnaire and the SSAGA family history module. Negative urgency will be defined as a latent independent variable, with individual item indicators from the UPPS-P negative urgency subscale. Sensitivity to alcohol will be defined as a latent independent variable with three measured variable predictors: Subjective, behavioral and electrophysiological sensitivity to 60mg/dl alcohol as compared to each individual's baseline response. The dependent measures of interest for sensitivity analysis include Subjective Response to Alcohol, Wisconsin Card Sort, and the Stop Signal Task. The dependent variable will be cumulative work performed for alcohol in the aversive session, defined as an observed variable. We will control for cumulative work performed for alcohol in the neutral session, as well as age, gender, and race, due to their relationship with alcohol use behaviors. Judgment of hypothesis viability will be assessed via **1**) fit indices (recommendations in parentheses: Root Mean Square Error of Approximation ( $RMSEA < 0.10$ ); Tucker Lewis Index ( $TLI > 0.95$ ); and Comparative Fit Index ( $CFI > 0.95$ ) and **2**) pathway loading significance.

**Hypothesis 4:** Significant factors from hypothesis 3 can identify a latent trait that classifies individuals into at two classes of individuals: those who have high and low SDA. The significant phenotypes from hypothesis 3 will be used in a latent class analysis to identify subgroups based on

**Figure 6. Proposed path analysis.** Covariates, error terms, and correlations not shown for simplicity

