their pattern of AUD risk. The Bayesian Information Criteria and entropy will be utilized to determine the number of latent classes that best fit the data. Individuals will be assigned to the latent class with the highest probability, and discrete class membership will be characterized using *post hoc* validators such as number of AUD criteria, negative urgency, family history density and lifetime drinking history. As a final validator, we will test if SDA is different between the classes to determine if class membership reflects motivation to work for alcohol in the face of aversive stimuli.

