### Aim 3 Hypothesis Testing Plan

***Hypothesis 5:*** *Those with greater SDA will demonstrate reduced event-related potential component amplitudes differences between negative vs. positive feedback about per-trial progress toward a reward.* We will employ a linear mixed model to test if SDA predicts positive and negative feedback-related N200 and P300 amplitude differences at baseline. Age, gender, biological family history of alcoholism density, and race will be used as covariates. We will explore a secondary linear mixed model analysis (co-varying for BrAC) using the ERP component differences between baseline and at **1**) maximum BrAC and **2**) terminal work for alcohol.

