***Hypothesis 6a:*** *Those with greater SDA will demonstrate greater resting state crosstalk (less differentiation) between the default mode and fronto-parietal networks.* Our preliminary results (Figure 5, above) suggest that advancing AUD severity increases communication between networks that are functionally independent (i.e., the default mode network is prominent at rest, while the fronto-parietal network is activated by focused mental activity). As we hypothesize that SDA marks increasing AUD severity, we similarly hypothesize that SDA is related to abnormally increased communication between the default mode and fronto-parietal networks. To test this hypothesis, whole-brain functional connectivity (FC) will be estimated for each individual participant using a data-driven, functionally based parcellation and characterized for segregation/modularity, which reflects the underlying organization into functional modules or communities. Age will be a covariate in all analyses. Furthermore, to characterize the tendency of brain regions to belong to the same module as a fine-grain continuum (as opposed to an integral membership), we use the consensus clustering approach. The pairwise correlations between module consensus and SDA of participants represent a mapping of SDA into the functional connectome domain. To control for false positives, the correlation between segregation/modularity (consensus clustering approach) and SDA will be z-normalized using 10,000 permutation tests, where the SDA vectors will be randomly shuffled and their associations with modularity consensus mapped 10,000 times, producing a distribution of expected SDA associations by chance. Based on the mean and standard deviation of this null distribution, the actual SDA associations can be z-scored and thresholded at  $p < 0.05$  (equivalent to a two tailed, i.e.,  $|z| > 1.96$ , for significant associations). To minimize false positives, we will also incorporate the equivalent of an extent threshold for network-based associations to account for the effect size (as measured by number of edges in connected components or by their spatial pairwise clustering) of the associations in the functional connectome domain. We will also consider using the Permutation Network Framework (PNF), which makes no assumptions about the distribution of the test statistics, since they often show non-standard distributions due to the intrinsic complex nature of brain connectivity data. To evaluate the robustness and reproducibility of these results, other gray matter parcellation schemes will also be assessed, using atlases that range from coarser to finer resolutions (from anatomically-based with 84 regions to multimodal with 360 regions, respectively). Using a similar approach, we will evaluate the associations between SDA and the network properties of integration and centrality. Integration reflects communication efficiency, often reflected by distance to closure

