
transformations of the shortest-path-lengths between nodes. Centrality measurements rank the relevant brain regions based on how central the nodes are and cover communicability aspects such as degree (number of edges per region) or the number of shortest-paths through each region (betweenness centrality).

**Hypothesis 6b:** *Those with greater SDA will demonstrate reduced ventral striatal-ventromedial frontal connectivity.* We will complement the connectome approach by using a seed-based approach to test voxel-level functional connectivity between the ventral striatum and ventromedial prefrontal cortex and its relation to SDA. For each subject, the functional connectivity between the ventral striatal seed (Figure 7d, red seed region) and all other cerebral gray matter voxels will be computed and transformed to MNI standard space for each subject. Age will be a covariate in all analyses. Finally, the resulting ventral striatal seed-to-gray-matter voxel-level FC estimations will be correlated (Pearson's coefficient) with subjects' SDA, yielding a high resolution (voxel-level) mapping of SDA onto fronto-striatal connectivity patterns. To control false positive findings, a multiple comparison correction based on false discovery rate will be applied ( $p_{FDR} < 0.05$ ) with an extent threshold ( $k=50$ ) to avoid spurious isolated voxels and small clusters.

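### Hypotheses 5 and 6 relate brain measures to aversive-session alcohol work with no neutral-session reference, so a positive result cannot by itself be attributed to seeking despite aversion; separately, session position is in neither Aim 1 model.

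*Combined protocol and SAP*

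**What the plan says.** All references are to the combined protocol and SAP, Section 7.0 (Statistical Considerations), unless stated.

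- **Score.** Under Hypothesis 1: "SDA will be defined as the amount of work performed (cumulative number of SDA trials completed) for alcohol rewards in the aversive session". It has no neutral-session or water reference.
- **Hypothesis 1.** Lifetime drinking history (LDH) predicts this score. "Age, gender, recent drinking history, and race will be included as covariates".
- **Hypothesis 2.** The alcohol-versus-water work ratio is modelled in both sessions. LDH (high or low), "stimulus type (aversive vs. neutral) and their interaction will be independent variables".
- **Hypothesis 3.** The outcome is the same aversive-session work, and LDH is among the predictors: "We will control for cumulative work performed for alcohol in the neutral session".
- **Hypothesis 5.** SDA predicts baseline feedback-related N200 and P300 differences. "Age, gender, biological family history of alcoholism density, and race will be used as covariates".
- **Hypotheses 6a and 6b.** SDA is related to network modularity and to ventral striatal connectivity. For both, "Age will be a covariate in all analyses". The 6b result is described as "yielding a high resolution (voxel-level) mapping of SDA onto fronto-striatal connectivity patterns".
- **Order.** Section 4.0 has the neutral and aversive sessions randomly counterbalanced. Neither Aim 1 model lists session position. The supplemental analyses name order for ERP and stop-signal measures; that list is open-ended, so an order analysis of work is not excluded, only not planned.

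**The concern.** Someone who works hard for alcohol in both sessions gets a high SDA score even if the aversive stimuli cut that work sharply. A brain measure that tracks willingness to work for alcohol under any condition would therefore satisfy Hypothesis 5 or 6. Aim 3 seeks the neural signature underlying SDA, so such a result could be reported as a marker of aversion resistance when it fits general drive equally well.

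The plan deals with this for LDH through Hypotheses 2 and 3, but Aim 3 has no counterpart. Its covariates do not include recent drinking either, which would be a partial proxy for drive.

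The session-position point is smaller. If work shifts between the first and second session, leaving position out adds noise to the within-person contrast on which Hypothesis 2 depends.

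**Working it through.** **Inputs.** The documents give no correlation of LDH or a brain measure with work by session, no between-session correlation (ρ) and no period effect (δ). All of these are assumed below. From the Power Analyses come r = 0.32 with n = 100, and d = 0.64 with 50 per group. The latter is a between-group figure borrowed here for the interaction. Section 4.0 scans only a subset, so n for Hypothesis 6 may be below 100. Calculations use two-sided α = 0.05 unless stated.

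**1. The plan's own figure.** Power ≈ Φ(atanh(r)·√(n−3) − z). With r = 0.32 and n = 100, atanh(0.32)·√97 gives 0.904 at α = 0.05 and 0.755 at the stated α = 0.01. For d = 0.64 and 50 per group, the noncentral t gives 0.887 and 0.716. The stated 0.90 is reproduced at 0.05 but not at 0.01. That is a separate matter and nothing below depends on it.

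**2. General drive only (Hypotheses 5 and 6).** Let a single brain measure X correlate 0.32 with work in both sessions, before covariates and before voxel or edge correction.

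- Raw aversive-session score: detected with probability 0.904, as in step 1.
- Aversive minus neutral: with equal variances, the correlation with X is (0.32 − 0.32)/√(2(1−ρ)) = 0, so rejection is at the nominal 5%. Simulation gave 0.048–0.051.
- Neutral work as covariate: the partial correlation is 0.32(1−ρ)/√((1−ρ²)(1−0.32²)).

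| ρ | Partial correlation | Detected, covariate form |
|---|---|---|
| 0.4 | 0.221 | 0.60 |
| 0.6 | 0.169 | 0.39 |
| 0.8 | 0.113 | 0.20 |

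The covariate removes only part of the shared drive, because one session measures drive with error. The difference is therefore the better main supporting analysis, with the covariate form as a check.

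**3. Price of the difference score.** Its variance is 2(1−ρ), which exceeds 1 (one session's variance) when ρ < 0.5. Suppose the true correlations are 0.32 aversive and 0.10 neutral. The correlation with the difference is 0.22/√(2(1−ρ)) = 0.201, 0.246 and 0.348 for ρ = 0.4, 0.6 and 0.8. Power is 0.52, 0.70 and 0.95.

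**4. Scale.** Section 5.0 (Schedule of Work) caps cumulative work at 850 correct trials (and 850 incorrect), and work cannot go below zero. In a simulation with general drive only (latent mean 350, SD 250, clipped to 0–850, ρ = 0.6), an additive aversion cut of 0.5, 1 or 1.5 SD made the raw difference significant in about 6, 17 and 43% of trials. The direction was that stronger drive looked more aversion-sensitive, which is opposite to the hypothesis. The 5% in step 2 thus holds for unbounded work only.

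**5. Session position, Hypothesis 2.** With balanced order, an omitted period effect δ adds δ² to the variance of the within-person difference. The standardised effect becomes 0.64/√(2(1−ρ)+δ²).

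| ρ | δ = 0 | 0.25 SD | 0.5 SD | 0.75 SD |
|---|---|---|---|---|
| 0.3 | 0.764 | 0.745 | 0.694 | 0.619 |
| 0.5 | 0.887 | 0.867 | 0.809 | 0.717 |
| 0.7 | 0.983 | 0.973 | 0.930 | 0.836 |

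**6. Session position, Hypothesis 1.** Only one session enters, so the omitted effect adds δ²/4. The correlation becomes 0.32/√(1+δ²/4) and power goes from 0.904 to 0.900, 0.885 and 0.861 for the same three effects.

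**The case against.** The strongest reply is that SDA is tested as the plan defines it. Hypothesis 4 describes the quantity as "motivation to work for alcohol in the face of aversive stimuli", and Hypothesis 6a is justified by SDA as a marker of AUD severity, not as an isolated aversion effect. On that reading general drive is part of the construct, and the harm lies only in how a result might later be described. This stands to the extent that Hypotheses 1, 5 and 6 are valid tests of what they state. It does not remove the gap: the plan itself uses the neutral session in Hypotheses 2 and 3, and gives no reason for leaving it out of Aim 3.

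A reader might infer more than the documents support:

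- *That Hypothesis 1 is invalid.* It tests the score as defined, and Hypothesis 2 supplies the aversion contrast for LDH.
- *That 90% is a false-positive rate.* It is the power to detect a correlation that was assumed to exist. For Hypothesis 6 it also precedes the planned permutation, extent-threshold and false-discovery-rate control.
- *That omitting session position biases the LDH effect.* Order is randomised, so only precision is at stake.
- *That Section 5.0 shows a period effect.* The instruction about second-session discharge time is a precaution for participants kept past 7:00 pm. It gives no evidence of a remaining shift in work.

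The difference score is also noisier at low between-session correlation and depends on scale. Both points are right, so it belongs in a supporting role.

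**Conclusion.** The point holds as a limit on attribution in Aim 3. As planned, a positive Hypothesis 5 or 6 cannot by itself distinguish seeking despite aversion from general drive for alcohol. Hypothesis 1 read alone has the same limit, but for LDH the Hypothesis 2 interaction already carries the aversion-specific question. There is no type I error inflation and no invalid test.

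Omitting session position is a secondary, precision-only matter. At an assumed ρ of 0.5 and d of 0.64, Hypothesis 2 interaction power falls from 0.89 to 0.87, 0.81 or 0.72 for period effects of 0.25, 0.5 or 0.75 SD. Nothing is lost if there is no period effect. The loss for Hypothesis 1 is at most about 0.04 over that range.

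The absence of a neutral-session term and of session position is plain from the text; the sizes rest on assumed correlations and period effects. The change is worth making before results are seen, because it is cheap and the choice of contrast afterwards would be open to question.

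**What to change.** 1. **Aim 1 models.** Add session position (first or second) as a within-person term in Hypothesis 2, and the position of the aversive session as a covariate in Hypothesis 1.
2. **Aim 3.** Keep Hypotheses 5 and 6 as stated. Prespecify one supporting analysis for each that replaces the SDA score with aversive-minus-neutral alcohol work, tested with the same error control as the main analysis. Repeat with aversive-session work adjusted for neutral-session work, as in Hypothesis 3, as a sensitivity check.
3. **Interpretation.** State that no result of Hypothesis 1, 5 or 6 is called aversion-specific on the raw score alone. For LDH, rest that claim on the Hypothesis 2 interaction. For Hypotheses 5 and 6, require the supporting contrast to be significant in the hypothesised direction. Add the caveat that work is bounded at zero and at the schedule maximum, so the contrast depends on scale.

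A more elaborate rule requiring agreement across raw, log and censored-data models is not advised: agreement in sign without significance is a weak criterion, and it is undefined for voxel-wise or edge-wise results.

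The cost is SAP wording, one degree of freedom in each Aim 1 model, and one supporting analysis with a sensitivity check for each of Hypotheses 5 and 6. Both sessions' work and the session order are already recorded. The main downside is power: the difference score is noisier than a single session when the between-session correlation is below 0.5, so a null supporting contrast should be reported as not separable from general drive, not as evidence against aversion specificity.

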Our long-term goal is to use SDA as a platform for the laboratory testing of novel pharmacologic and behavioral interventions that can be used among those with the highest risk, but who have yet to progress to treatment-resistant drinking. The objective of this project is to test SDA across multiple levels of analysis. We consider SDA as an early marker of alcohol use disorder progression that is related to lifetime drinking history, alcohol use disorder risks, and brain physiology. Our current IARC pilot study (IRB #) demonstrates that SDA can be objectively quantified via an intravenous alcohol self-administration task, where operant work for identical incremental alcohol rewards is paired with aversive stimuli. Our preliminary data support our central hypothesis: that behavior in the SDA model is attributable to lifetime alcohol exposure, is related to alcohol use disorder (AUD) risk factors and phenotypes, and reflects alterations in neural system function. Specifically, they suggest that the degree of SDA is positively associated with recent drinking history, negative affect-based rash action (i.e. negative urgency, including action with respect to alcohol use), and self-rating of the effects of alcohol. The rationale for this work is that it would lead to the first objective, well-validated measure of SDA in humans.

Our specific aims are to:

*Aim 1:* Characterize SDA as a function of lifetime drinking history.

*Hypothesis 1:* Greater SDA will reflect greater lifetime drinking history.

*Hypothesis 2:* Those with a high lifetime drinking history will demonstrate less sensitivity to aversion in the preference to work for alcohol. Specifically, those with a high lifetime drinking history will work more for alcohol compared to water under both aversive and neutral experimental conditions, whereas those with a low lifetime drinking history will only work more for alcohol compared to water when alcohol seeking is paired with neutral stimuli.

Aim 2: Quantify associations between SDA and alcohol use disorder severity, and between SDA and risk phenotypes; then characterize how these risk factors classify individuals into those who will and will not work for alcohol in the context of aversive stimuli.

*Hypothesis 3:* Those with greater SDA will have greater AUD severity, greater negative urgency, a greater density of familial alcoholism, and reduced subjective, behavioral, and electrophysiologic sensitivity to alcohol.

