### Power Analyses

Alcohol self-administration: Our previous alcohol self-administration work showed effect sizes from 0.49 to 1.31 according to the phenotype of interest. Neurophysiological correlates (EEG/fMRI): Published outcome and feedback-related differences in N200 and P300 amplitudes yield effect sizes from 0.78 to 2.12 for subjects with an AUD versus controls, and 0.62 to 1.6 for the effect of alcohol. There are no standards for power analyses in whole brain connectomics. However, our pilot data showed significant results in  $n=51$ , suggesting  $n=100$  is sufficient to find robust connectivity patterns. We will ensure robustness using permutation tests combined with an extent threshold, or alternatively, using the Permutation Network Framework. Relationship to AUD risk variables: In our pilot data, the relationship between SDA and AUD risk correlates ranged from  $r=0.32 - 0.63$ . With a sample of  $n=100$ , we can detect an effect size of at least 0.32 and still maintain adequate  $power=0.90$ ,  $\alpha=0.01$ . When categorized by groups of  $n=50$  (high/low lifetime drinking history), we can detect differences with an effect size of 0.64 and still maintain adequate  $power=0.90$ ,  $\alpha=0.01$ .

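### Hypothesis 2 predicts a preference for alcohol over water in three of four group-by-session cells, but no test or interval against zero is planned, and the follow-ups carry an unneeded condition

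*Combined protocol and SAP*

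**What the plan says.** Hypothesis 2 appears in section 2.0 and again in section 7.0 (Aim 1 Hypothesis Testing Plan). It opens with a general claim, that high-LDH participants are less sensitive to aversion, and then makes it specific. High-LDH participants are to prefer alcohol in both sessions. For the other group, section 7.0 says "those with a low lifetime drinking history will only work more for alcohol compared to water in the neutral session", and section 2.0 says "those with a low lifetime drinking history will only work more for alcohol compared to water when alcohol seeking is paired with neutral stimuli".

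The outcome is R, work for alcohol minus work for water divided by their sum, computed separately for the aversive session (R_a) and the neutral session (R_n). The model is a repeated-measures mixed model in which "lifetime drinking history (high vs. low), stimulus type (aversive vs. neutral) and their interaction will be independent variables". Adjustment is made for race, gender, age and recent drinking.

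Follow-up is conditional: "If lifetime drinking history and the interaction with stimulus are significant predictors of the ratios of work performed, we will conduct follow-up planned contrasts". Those contrasts are described as "follow-up planned contrasts to examine the ratios separately for the neutral and aversive sessions to test high and low lifetime drinking history".

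Neither the Power Analyses nor the supplemental and exploratory analyses add a test, interval or cell estimate of R against 0. The nearest power statement concerns two groups of 50: "we can detect differences with an effect size of 0.64".

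**The concern.** Working more for alcohol than for water is the same statement as R above 0. The specific prediction is therefore about four cell means relative to zero, while everything the plan names compares cells with one another. A trial that follows the plan can find the interaction and still have no planned result on whether high-LDH drinkers prefer alcohol under aversion, or whether low-LDH drinkers prefer it only in the neutral session. If the follow-ups are reached, a high-low difference in R_a is compatible with both groups preferring alcohol, or with neither doing so.

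The follow-ups also require a significant LDH effect. The prediction needs no overall LDH effect, so the condition can block follow-up when the prediction is true.

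**Working it through.** **1. The prediction as cell means.** R has the sign of alcohol work minus water work. Write H and L for high and low LDH, A and N for aversive and neutral. The prediction is HN > 0, HA > 0, LN > 0, and LA not above 0.

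**2. What the stated terms measure.**
- LDH, averaged over sessions: [(HA + HN) − (LA + LN)]/2
- Stimulus: [(HA + LA) − (HN + LN)]/2
- Interaction: (HA − HN) − (LA − LN)
- High-low contrast by session: HA − LA and HN − LN

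Add a constant c to all four cells and it cancels in every line. None of these can locate a cell relative to 0.

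**3. The plan's own figure.** Effect size 0.64 with 50 per group is stated to give power 0.90 at alpha 0.01. A two-sided t-test gives 0.716 at alpha 0.01 and 0.887 at 0.05. That discrepancy is a separate matter. The Hypothesis 2 plan states no alpha; I use two-sided 0.05 below.

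**4. Illustration of the missing test.** The documents give the group size and the 0.64. My assumptions are normal R, SD 1 per session, within-person correlation 0.5, a neutral-session group difference of 0, and no covariates. Simulated results (40,000 runs per pattern):

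| HA / HN / LA / LN | Interaction | High-low contrast in R_a | All three predicted cells shown above 0 |
|---|---|---|---|
| 0.64 / 0.64 / 0 / 0.64 (prediction true) | 0.88 | 0.88 | 0.98 |
| 1.00 / 1.00 / 0.36 / 1.00 (all cells prefer alcohol) | 0.89 | 0.89 | 1.00 |
| 0 / 0 / −0.64 / 0 (no cell prefers alcohol) | 0.89 | 0.89 | 0.00 |

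The planned comparisons behave alike in all three. The cell tests separate the third pattern from the first. The low/aversive interval separates the second: its half-width is about 2.01/√50 = 0.28, so an interval centred on 0.36 runs from 0.08 to 0.64 and excludes 0.

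**5. The LDH condition.** Same assumptions, aversive difference 0.64, neutral difference 0.
- Interaction: 0.64 − 0 = 0.64; SD √(2(1 − 0.5)) = 1; noncentrality 0.64 × √(50/2) = 3.20; 98 df; power 0.887.
- LDH averaged over sessions: 0.64/2 = 0.32; SD √((1 + 0.5)/2) = 0.866; noncentrality (0.32/0.866) × 5 = 1.85; power 0.448. Sums and differences are uncorrelated under equal variances, so the joint probability is 0.887 × 0.448 = 0.397.
- LDH coded as the neutral-session effect: the true effect is 0, so LDH is significant only 0.05 of the time; joint about 0.04 (simulation).
- LDH coded as the aversive-session effect: joint about 0.81 (simulation).

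**6. Sensitivity under session-averaged coding (joint against interaction alone).**
- Correlation 0.2: 0.38 against 0.71. Correlation 0.7: 0.40 against 0.98.
- Alpha 0.01: 0.16 against 0.72.
- Neutral difference 0.1, 0.2, 0.32: 0.43 against 0.76; 0.39 against 0.59; 0.28 against 0.35.
- A crossover that meets the prediction (HN and HA 0.3, LN 0.9, LA −0.3): about 0.05 against about 1.00. Both groups average 0.3, so there is no overall LDH effect to find.

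**The case against.** The strongest reply is that the lead claim of Hypothesis 2 is an LDH-by-stimulus interaction, which the plan tests without any condition. That stands. A reader might infer that Hypothesis 2 is untested altogether; the documents do not support that. The gap is confined to the specific pattern.

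Second, the fitted model can supply the four cell means, and the follow-up wording is loose enough to cover looking at each group within a session. Both are fair, and they make the repair cheap. But no reference value of 0 is stated on either reading, and leaving the tests and covariate values to be chosen after the data are seen is avoidable. Misreading a high-low difference in R_a as confirmation is a risk, not something the plan says it will do.

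Third, a reader might infer that the LDH condition cuts follow-up from 0.89 to 0.40. That is one coding among several, and the plan names none; the range is from almost no loss to almost complete loss.

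Fourth, a reader might infer that unconditional cell tests could carry Hypothesis 2 alone. With HA 0.64, LA 0 and LN 0.64, the chance that all three predicted cells exceed 0 while the interaction is missed is 0.11 when the neutral difference is 0 and 0.64 when it is 0.32. Most of that rise comes from the assumed interaction shrinking to 0.64 − 0.32 = 0.32, where its power is 0.35. Positive cells without an interaction do not show that the groups differ.

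Finally, section 7.0 calls LDH the predictor "lifetime drinking history is the independent variable, as in hypothesis 1", where it is continuous, and then high versus low. The first phrase may only name the same questionnaire measure. This is a separate wording gap and adds no weight here.

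**Conclusion.** The point holds for the specific prediction and should be fixed. That part rests on the text and on the algebra in step 2, not on any assumed SD or correlation: the plan states no test or interval of R against 0, and its stated comparisons cannot provide one. The unconditional interaction test of reduced sensitivity to aversion is sound.

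The LDH condition is poorly matched to the prediction, but its cost cannot be fixed from the documents. With 50 per group, SD 1, correlation 0.5, differences of 0.64 (aversive) and 0 (neutral) and alpha 0.05, follow-up is reached with probability of roughly 0.04 to 0.81 depending on coding, against 0.89 on the interaction alone. These are illustrations: R is bounded at −1 and 1, and the documents give no SD, correlation or LDH effect for it.

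**What to change.** In the Hypothesis 2 plan:

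1. Report mean R with a confidence interval in all four cells whatever the model tests show, from the fitted model at stated covariate values (for example, overall sample means), with unadjusted means alongside.
2. Test R against 0 in the three cells where preference is predicted. For low/aversive, give the interval and do not read non-significance as absence of preference.
3. Drop the LDH condition, so that high-low contrasts within session follow the interaction alone.
4. State that support for the specific pattern needs the interaction together with the cell results.
5. As a consequential wording point, say that Hypothesis 2 uses LDH as high versus low, and how participants outside both kg ranges, whom sections 3.0 and 4.0 admit at the investigator's discretion, enter it.

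The cost is wording and a few more cell-level tests, on the same data and model. Precision is workable. Unadjusted with n = 50, power against 0 is 0.79 at a mean of 0.4 SD and 0.93 at 0.5 SD. Adjusted to overall covariate means, with groups differing by 0, 1 or 2 SD on two covariates (such as age and recent drinking), the half-width is 0.28, 0.32 or 0.40 SD and power at 0.5 SD is 0.94, 0.87 or 0.69. That is why the covariate values should be fixed in advance and unadjusted means shown.
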